2. OBJECTIVES

Primary Objectives

To evaluate the effects of 12 weeks of structured physical exercise (chair-based PEROSI protocol) followed by 4 weeks of social heterochronic parabiosis (SHP)-based intergenerational

intervention on frailty syndrome and serum mature brain-derived neurotrophic factor (mBDNF) levels in community-dwelling elderly with physio-cognitive decline syndrome (PCDS).

Secondary objectives

- To analyze the effects of the combined intervention over 16 weeks on hand grip strength in elderly with PCDS.
- To analyze the effects of the combined intervention over 16 weeks on gait speed in elderly with PCDS.
- To analyze the effects of the combined intervention over 16 weeks on cognitive function as measured by the MoCA-Ina score in the elderly with PCDS.
- To evaluate the effects of the combined intervention over 16 weeks on health-related quality of life in the elderly with PCDS.
- To assess correlations between changes in serum mBDNF levels and changes in MoCA-Ina score, hand grip strength, and gait speed in the elderly with PCDS.

Hypothesis

Elderly people with physio-cognitive decline syndrome (PCDS) who receive 12 weeks of structured physical exercise followed by 4 weeks of social heterochronic parabiosis (SHP)-based intergenerational intervention on top of nutritional education have significantly better frailty syndrome status and higher serum mature brain-derived neurotrophic factor (mBDNF) levels than those receiving nutritional education alone after 16 weeks of intervention, along with greater improvements in hand grip strength, gait speed, cognitive function (MoCA-Ina score), and health-related quality of life.

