7. METHODS

7.1 Study parameters/endpoints

7.1.1 Main study parameter/endpoint

- Change in frailty syndrome status (assessed using Cardiovascular Health Study criteria: score 0 robust, 1–2 pre-frail, ≥3 frail) from baseline to week 16.
- Change in serum mature brain-derived neurotrophic factor (mBDNF) levels (measured by ELISA) from baseline to week 16.

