7.1.2 Secondary study parameters/endpoints

- Change in hand grip strength (in kilogram; dominant hand, best of 3 trials using hand dynamometer) from baseline to week 16.
- Change in gait speed (m/s; average of 2 trials over 6-meter walk test) from baseline to week 16.
- Change in cognitive function (MoCA-Ina total score, range 0–30) from baseline to week 16.
- Change in health-related quality of life (SF-12 questionnaire) from baseline to week 16.
- Correlations between changes in serum mBDNF levels and changes in MoCA-Ina score, hand grip strength, and gait speed.

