9. STATISTICAL ANALYSIS

All collected data will be initially recorded on research case report forms (CRFs) and subsequently transferred to secure electronic storage for data cleaning, coding, and verification. Descriptive data and analytical results will be presented in narrative text, tables, or figures as appropriate.

Normality of data distribution will be assessed using the Kolmogorov-Smirnov or Shapiro-Wilk test ($p > 0.05$ indicates normal distribution). Normally distributed continuous data will be presented as mean \pm standard deviation (SD); non-normally distributed data as median with minimum-maximum range. Categorical data will be presented as frequencies and percentages. Statistical significance will be set at $p < 0.05$. All analyses will be performed using SPSS version 20 software.

Primary analyses will be conducted on the per-protocol (PP) population, excluding drop-out subjects. Between-group comparisons of changes in study outcomes (hand grip strength, gait speed, MoCA-Ina score, serum mBDNF levels, and health-related quality of life) will use unpaired t-tests (parametric) or Mann-Whitney U tests (non-parametric), selected based on normality test results.

Correlations between serum mBDNF levels and MoCA-Ina score, hand grip strength, and gait speed will be evaluated using Pearson correlation (for normally distributed variables) or Spearman correlation (for non-normally distributed variables), according to normality assessment of each variable.

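### The secondary endpoint correlates changes in mBDNF with changes in function, but section 9 plans to correlate levels with scores

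*Combined protocol and SAP*

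**What the plan says.** The last secondary objective in section 2 is "To assess correlations between changes in serum mBDNF levels and changes in MoCA-Ina score, hand grip strength, and gait speed in the elderly with PCDS". The matching endpoint in section 7.1.2 uses almost the same words: "Correlations between changes in serum mBDNF levels and changes in MoCA-Ina score, hand grip strength, and gait speed". Sections 7.1.1 and 7.1.2 give each of the four component changes a time window. For mBDNF it is "Change in serum mature brain-derived neurotrophic factor (mBDNF) levels (measured by ELISA) from baseline to week 16", for gait speed "Change in gait speed (m/s; average of 2 trials over 6-meter walk test) from baseline to week 16", and grip strength and MoCA-Ina run over the same period.

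Section 9 has one paragraph on this endpoint. It begins "Correlations between serum mBDNF levels and MoCA-Ina score, hand grip strength, and gait speed will be evaluated using Pearson correlation", with Spearman as the alternative, chosen by the normality of each variable. It does not mention change and names no visit. The paragraph just before it does refer to change, for the group comparisons: "Between-group comparisons of changes in study outcomes".

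**The concern.** A correlation of levels asks whether people with higher mBDNF also score better. A correlation of changes asks whether people whose mBDNF rose also improved. The objective is the second question; section 9, as written, answers the first. An analyst could follow section 9 exactly and never compute the declared endpoint.

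The literal reading is also underspecified. Section 7.3 places assessments at weeks 0, 12 and 16, so three outcomes at three visits allow 3 × 3 = 9 level correlations, with none singled out. The choice between Pearson and Spearman is affected too, because levels and change scores can have different distributions. If this is left open, the choice between level and change results could be made after the data are seen.

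**Working it through.** **Text.** Section 2: change against change. Section 7.1.2: change against change. Section 9: levels against scores. No other section specifies an analysis for this endpoint, so nothing resolves the difference.

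**Plan's own figures.** No sample size or power is stated for the correlations. Section 4.5 gives a largest requirement of 42 per group, and section 7.6 allows up to 15% dropout: 42 / (1 − 0.15) = 49.4, rounded up to the planned 50. The illustration below uses 2 × 42 = 84 analysed.

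**How far levels and changes can differ.** The documents give no correlations, so all inputs here are assumed. Take equal variances at both visits, test-retest correlation S for both variables, same-visit correlation r and cross-visit correlation c. With unit variances, the covariance of the two changes is 2r − 2c and each change has variance 2 − 2S, so

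change correlation = (r − c) / (1 − S).

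With r = 0.20 and S = 0.7:
- c = 0.20: 0 / 0.3 = 0
- c = 0.15: 0.05 / 0.3 = 0.167
- c = 0.10: 0.10 / 0.3 = 0.333

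Simulation (40,000 trials, n = 84, two-sided test at 5%) gave these rejection rates:

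| c | Change correlation | Level test | Change test |
|---|---|---|---|
| 0.20 | 0 | 45.1% | 5.2% |
| 0.15 | 0.167 | 44.8% | 32.9% |
| 0.10 | 0.333 | 45.0% | 87.9% |

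The level test cannot tell the three cases apart. The change-test rates depend on S, for the same three values of c:

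| S | Change correlations | Change test |
|---|---|---|
| 0.5 | 0 / 0.10 / 0.20 | 5.1 / 14.9 / 44.8% |
| 0.7 | 0 / 0.167 / 0.333 | 5.2 / 32.9 / 87.9% |
| 0.85 | 0 / 0.333 / 0.667 | 5.2 / 88.2 / 100% |

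**Second model.** Let each measurement be a stable personal value plus visit-specific variation. Then level correlation = ICC × r_between + (1 − ICC) × r_within, while change correlation = r_within. With ICC 0.7:
- r_between 0.5, r_within 0: level 0.7 × 0.5 = 0.35, change 0.
- r_between 0, r_within 0.5: level 0.3 × 0.5 = 0.15, change 0.50.

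The two agree only when r_between equals r_within.

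**Pooling the arms (a side issue).** If treatment shifts both changes by d standard deviations and there is no link within arms, the pooled change correlation is (d²/4) / (1 + d²/4). Forty-two per group at 80% power corresponds to d = (1.960 + 0.842) × √(2/42) = 0.611. Taking d = 0.61 on both gives 0.093 / 1.093 = 0.085, and Pearson is significant in about 12% of trials. The rate is about 5% at d = 0.3 and 46% at d = 1.0. Adjusting for arm brings it back to about 5% throughout.

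**The case against.** The best defence is that section 9 is shorthand. The protocol uses the word levels as part of the variable's name even when it means change, as in the endpoint itself. The section 9 sentence follows the section 7.1.2 bullet in the same variable order with the references to change left out. Objective and endpoint agree with each other, and section 9 names no visit for a level analysis. This reading is plausible. It does not settle the matter, because the neighbouring paragraph does say changes and no text tells the analyst to carry that over.

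The illustration also has a weak point. It assumes equal variances at both visits, but section 4.2 restricts baseline MoCA-Ina to 22–26. With that truncation (assumed mean 24, SD 2.5 to 4), the week-16 level test rejects in about 16–21%, 26–30% and 39–41% for c = 0.20, 0.15 and 0.10. So the flat 45% does not hold for MoCA-Ina, and at c = 0.15 the two tests nearly coincide. They still diverge clearly in the other two cases.

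The arm-adjustment point is separate from levels versus changes, and its effect sizes are assumed: the 9 to 42 per group in section 4.5 implies d from about 0.61 to (1.960 + 0.842) × √(2/9) = 1.32. It stands only as a suggestion. This is also the last-listed secondary objective and has no stated power, which limits the weight of the whole point.

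**Conclusion.** The concern holds. The stated analysis does not match the stated objective and endpoint, and no other text reconciles them. That conclusion rests on the wording alone. The numbers show only that the mismatch can matter: under assumed inputs, one level correlation of 0.20 is compatible with change correlations from 0 to 0.33 at S = 0.7, or from 0 to 0.67 at S = 0.85. Confidence is high that the texts disagree; whether a level analysis was really intended cannot be known from the documents. The group comparisons, sample size and visit schedule are unaffected. It should be corrected before the data are analysed, but it does not threaten the trial's main result.

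**What to change.** Replace the section 9 sentence with wording such as:

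> For serum mBDNF and for each of MoCA-Ina score, grip strength and gait speed, the change from baseline to week 16 will be calculated. The correlation of the mBDNF change with each of the other three will be estimated with a 95% CI, by Pearson or Spearman according to the normality of the change scores, in the same analysis population as the group comparisons.

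Add the baseline-to-week-16 window to the correlation bullet in section 7.1.2, and label any level or week-12 correlations exploratory. Section 3 (intention-to-treat with per-protocol sensitivity) and section 9 (per-protocol primary) disagree on the analysis population. That is a separate matter, and this sentence would follow whatever is settled there.

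Optionally, report an arm-adjusted partial correlation beside the pooled one. It costs almost no precision: at n = 84 and r = 0.30, the Fisher 95% CI is 0.091 to 0.483 pooled (standard error 1/√81) and 0.090 to 0.484 adjusted (1/√80).

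The cost is one sentence and one phrase, plus a little analysis work if the adjusted correlation is added. No new data, visits or participants are needed.

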4.5 Sample size calculation

The sample size was calculated to detect clinically meaningful differences between the intervention and control groups in key outcome measures, including handgrip strength, gait speed, cognitive function (MoCA-Ina score), health-related quality of life (SF-12), and serum mature brain-derived neurotrophic factor (mBDNF) levels.

Sample size estimation was performed using the formula for comparison of two independent means, with a two-sided significance level (α) of 5% and a statistical power ($1-\beta$) of 80%. The standard deviation and expected mean differences for each outcome were derived from previously published studies involving older adults, as no prior studies have specifically evaluated SHP-based interventions or their combination with structured physical exercise.

Based on these calculations, the required sample sizes for individual outcome parameters ranged from 9 to 42 participants per group. Considering the largest estimated sample size requirement and allowing for potential dropouts, the minimum required sample size for this randomized controlled trial was determined to be 100 older adult participants, with **50 participants allocated to each group (intervention and control)**.

This sample size is considered sufficient to evaluate the primary and secondary outcomes of the study and to ensure adequate statistical power while accounting for potential attrition during the study period.

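### The mBDNF–function correlations have no term for treatment arm, so an effect of the intervention on both measures can by itself produce a correlation

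*Combined protocol and SAP*

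**What the plan says.** The correlation is a listed secondary objective in Section 2: "To assess correlations between changes in serum mBDNF levels and changes in MoCA-Ina score, hand grip strength, and gait speed in the elderly with PCDS". Section 7.1.2 repeats it as a secondary endpoint: "Correlations between changes in serum mBDNF levels and changes in MoCA-Ina score, hand grip strength, and gait speed".

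The only analysis text is one sentence in Section 9. It names the variables as "Correlations between serum mBDNF levels and MoCA-Ina score, hand grip strength, and gait speed" and says they "will be evaluated using Pearson correlation (for normally distributed variables) or Spearman correlation", the choice depending on normality tests. It mentions no stratification, covariate or partial correlation.

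The hypothesis in Section 2 is that, after 16 weeks, the intervention arm has higher serum mBDNF than the control arm, "along with greater improvements in hand grip strength, gait speed, cognitive function (MoCA-Ina score), and health-related quality of life".

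Two items might look like an adjustment. ANCOVA is in the list of abbreviations, and Section 7.3.9 gives the Charlson index a role in adjusting for confounding. Neither is tied to the correlations, and neither removes a difference between arms.

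**The concern.** Under the trial's own hypothesis, treatment arm is a common cause of the mBDNF change and the functional change. The two arms then form two clouds of points, one shifted up and to the right of the other. A single coefficient through both clouds is positive even if, inside each arm, participants with larger mBDNF gains do no better on function than the rest. The more successful the intervention, the larger this component.

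The protocol presents mBDNF as a marker of neuroplasticity and of the link between muscle and brain. This correlation is the only planned analysis that relates mBDNF to function at the level of the individual participant. A significant unadjusted coefficient could do no more than restate that both outcomes responded to treatment, which the between-group tests in Section 9 already address.

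**Working it through.** **Inputs from the documents**

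- Section 4.5: "Sample size estimation was performed using the formula for comparison of two independent means", two-sided 5%, 80% power. Requirements across the outcomes "ranged from 9 to 42 participants per group". No mean difference or SD is given.
- Section 7.6: drop-out of up to 15%.
- Section 3: 1:1 allocation, 50 per arm.
- Section 9: primary analyses on the per-protocol population, excluding drop-outs.

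**The plan's own figure.** 42/(1 − 0.15) = 49.4, rounded up to 50 per group and 100 in total. This agrees with Section 4.5. In reverse, 50 × 0.85 = 42.5, so about 42 per arm would be analysed.

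**Implied effect sizes (an assumption).** Inverting the normal-based formula for two means gives d = (1.960 + 0.842) × √(2/n):

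- n = 42: d = 2.802 × 0.218 = 0.61
- n = 9: d = 2.802 × 0.471 = 1.32

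**Correlation due to arm alone.** Take equal arms, zero correlation within each arm, and arm differences of d1 (mBDNF change) and d2 (functional change) in within-arm SDs. The correlation over both arms is

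r = (d1·d2/4) / √[(1 + d1²/4)(1 + d2²/4)]

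- d1 = d2 = 0.61: 0.0933/1.0933 = 0.085
- d1 = 0.61, d2 = 1.32: 0.2017/√(1.0933 × 1.4361) = 0.2017/1.2530 = 0.16
- d1 = d2 = 1.0: 0.25/1.25 = 0.20
- d1 = d2 = 1.32: 0.4361/1.4361 = 0.30
- either d = 0: r = 0

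**How often the test rejects.** Simulation with normal data, zero within-arm correlation, a two-sided 5% Pearson test and 40,000 trials per setting:

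| d1, d2 | r from arm alone | Unadjusted, 42 per arm | Unadjusted, 50 per arm | Partial, given arm |
|---|---|---|---|---|
| 0, 0.61 | 0 | 5% | 5% | 5% |
| 0.3, 0.3 | 0.02 | 5% | 5% | 5% |
| 0.5, 0.5 | 0.06 | 8% | 9% | 5% |
| 0.61, 0.61 | 0.085 | 12% | 13% | 5% |
| 0.8, 0.8 | 0.14 | 24% | 28% | 5% |
| 0.61, 1.32 | 0.16 | 32% | 37% | 5% |
| 1.0, 1.0 | 0.20 | 45% | 52% | 5% |
| 1.32, 1.32 | 0.30 | 83% | 90% | 5% |

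The simulation used Pearson. The rates for Spearman were not computed, but the mechanism is the same, because ranks taken over both arms also shift with arm.

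**Which variables are affected.** Section 9 speaks of levels, while Sections 2 and 7.1.2 speak of changes. The problem arises for changes and for post-intervention levels. It does not arise for baseline levels, which are measured before randomisation.

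**The case against.** **Pooling is not stated.** A reader might infer that the objective, the endpoint and Section 9 all define one pooled analysis set. They do not. Only the objective names the elderly with PCDS, and the neighbouring objectives on grip, gait, MoCA-Ina and quality of life use similar wording although the hypothesis treats them as two-arm comparisons. The plan is silent on arm. This stands as a limit on the wording, but not as a defence: an unstratified coefficient with no arm term is what the sentence in Section 9 produces, and silence leaves the choice open after the data are seen.

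**The size is uncertain.** A reader might take the largest rates as what the plan implies. They are not. The range of 9 to 42 spans five outcomes, including SF-12, which is not in these correlations, and the documents do not say which outcome needs which number. The 83% requires both mBDNF and the functional measure to sit at the smallest requirement; the 12% requires both to sit at the largest. One measure at each extreme gives 32%. The planning effects also come from other studies, and whether their SDs refer to changes or levels is not stated. All of this stands.

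**A pooled correlation is not false.** If both measures shift with arm, the correlation over both arms really is non-zero, so detecting it is not a Type I error for that quantity. The documents promise only to assess correlations and claim neither mediation nor surrogacy. This also stands, and it places the problem in interpretation: the rates in the table are errors only if the coefficient is read as a link that exists apart from treatment.

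**The endpoint is minor.** It is the last secondary endpoint, and neither the sample size nor any between-group comparison depends on it. That limits the weight of the point, but the correction costs almost nothing.

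**Conclusion.** The point holds. As written, Section 9 gives an unadjusted coefficient for a listed secondary endpoint, and the trial's own hypothesis creates the condition under which that coefficient can be non-zero with no association within either arm.

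Its size cannot be fixed from the documents. With assumed effects of 0.61 to 1.32, about 42 per arm, normal data and zero within-arm correlation, the unadjusted 5% test rejects in roughly 12% to 83% of trials. The inflation is slight at 0.5 on both measures (8%), negligible at 0.3 on both, and absent if the intervention moves only one of the two.

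Two stronger inferences are not supported. The documents do not show that the trial's efficacy conclusions are at risk, since the randomised between-group comparisons do not use these coefficients. Nor is the missing quantity a link within individual people: with changes taken from baseline to week 16, each participant contributes one pair of changes, so the relevant contrast is between participants in the same arm.

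**What to change.** In Section 9:

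- State that the endpoint is the correlation of changes, in line with Sections 2 and 7.1.2.
- Analyse it as a partial correlation adjusted for treatment arm, Pearson or Spearman on ranks.
- Report the coefficient within each arm and a scatter plot marked by arm beside it.
- If an unadjusted coefficient over both arms is also shown, say that it is not evidence of a biomarker–function link independent of treatment.

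This takes a sentence or two, needs no new data and costs one degree of freedom. With 84 participants and a true within-arm correlation of 0.3, approximate power is 79% for the adjusted analysis, against 80% for a simple correlation of the same size (Fisher z: 0.3095 × √80 − 1.96 = 0.81, against 0.3095 × √81 − 1.96 = 0.83).

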10. ETHICAL CONSIDERATIONS

This study will be conducted in accordance with the principles of the Declaration of Helsinki (2013 revision), Good Clinical Practice (GCP) guidelines, and applicable Indonesian regulations for clinical research involving human subjects. The protocol, informed consent forms (for elderly participants and orphanage representatives for children), and all study-related materials have been submitted for review and approval by the Komite Etik Penelitian Kedokteran Fakultas Kedokteran Universitas Indonesia – Rumah Sakit Cipto Mangunkusumo (KEPK FKUI-RSCM) or the relevant institutional ethics committee. The study will not commence until written approval is

obtained. Any amendments to the protocol will be submitted for ethical review and approval prior to implementation.

10.1 Recruitment and informed consent

Eligible elderly participants will be informed about the study purpose, procedures, potential risks, benefits, voluntary nature, and right to withdraw at any time without consequence through verbal explanation and written information sheets. Informed consent will be obtained in writing by the principal investigator or trained research assistant, with opportunity for questions. If needed, family members or caregivers may accompany the participant during consent, but the decision remains with the participant.

For child participants (intervention arm only), written permission will be obtained from the orphanage management (as legal guardian representative). Child-friendly verbal explanations will be provided to children, and assent will be sought based on their understanding and willingness. Children may refuse or withdraw at any time.

10.2 Vulnerable subjects

This study involves two vulnerable groups:

- Elderly (geriatric) participants: Aged 60–75 years with physio-cognitive decline syndrome (PCDS), screened for adequate comprehension (MoCA-Ina 22–26, IADL >5). Protection measures include clear, repeated explanations (with family/caregiver if desired), assurance of voluntariness, close monitoring for discomfort, and immediate withdrawal option.
- Children (aged 5–8 years from orphanages): Recruited only for low-risk intergenerational activities. Protection includes orphanage guardian consent, child-friendly preparation and explanations, constant on-site supervision by research team and orphanage staff, post-session reflection for emotional well-being, and unrestricted right to refuse or stop participation.

